Smoking Status: At least 100 cigarettes in entire life	National Health Interview Survey 
Smoking Status: Years as a smoker	Lung Cancer Screening Decision Tool 
Smoking Status: Current smoking	Current MSK Survivorship Patient Assessment (Based on the National Health Interview Survey)
Cigarettes per day	Current MSK Survivorship Patient Assessment
Alcohol use	The CAGE questionnaire 

**4.2.2 The Treatment Checklist** (Appendix B) collects claims data about the head and neck cancer diagnosis and treatment, which will then be translated into lay language. This will be done differently at the two participating sites. At MSK, HN-STAR generates an Automated Treatment Checklist, which presents an organized list of diagnosis, staging and treatment received at MSK using claims data from billing codes in the MSK record. The NP is prompted to verify the accuracy of the presented list and make necessary corrections. At HH, where claims data will not be automatically ported to HN-STAR, there is a Manual Treatment Checklist, in which all possible diagnosis and treatment options are presented as an organized checklist. The NP must manually complete the Manual Treatment Checklist by referring to the patients' medical records. At either institution, once a patient has agreed to participate in the study, prior to the participant's survivorship clinic visit, the NP will verify or complete the checklist. The checklist will result in the generation of a lay language treatment summary that will appear in the Survivorship Care Plan (described below in section 4.2.4). The NPs at both sites will be trained on how to use the Treatment Checklist.

**4.2.3 The Interactive Discussion Guide** (Appendix M) integrates data from the Survivor Self-Assessment, data from the Treatment Checklist, and data regarding evidence-based survivorship care. Three algorithms will then use these data to generate the Interactive Discussion Guide that the NP can use during the routine visit.

1. *Treatment algorithms* use Current Procedural Terminology (CPT) codes and National Comprehensive Cancer Network (NCCN) guidelines to generate personalized surveillance recommendations (e.g., annual thyroid studies for survivors who received radiation to neck).

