**Physical exam**

- Assess for increased neck size or obesity indicating possible causes of sleep apnea

**Recommendations for evaluation and management** (Check all that apply.)

- Referral to primary care provider
- Sleep log
- Sleep hygiene review (routine of bed time and awakening, light exposure, avoiding naps, and only being in bed to sleep)
- Consider discontinuing or reducing use of steroids, opioids, anti-depressants.
- Physical activity (moderate aerobic exercise for 2.5 hours a week and strength training 2-3 days a week)
- Referral to psychology (MSK)
- Referral to psychology (outside)
- Referral to integrative medicine (MSK)
- Prescription for sleep aide
- Patient education material on sleep
- Video on sleep
- Not discussed because chronic and previously addressed
- Other (Note names of providers or other details not described above)

**4.2.4** Finally, the **Survivorship Care Plan** will present a treatment summary and plan of care. HN-STAR generates a Survivorship Care Plan after each visit (See template in Appendix C). The treatment summary contains a plain-language cancer history. The plan of care contains personalized recommendations for cancer surveillance, management of late effects, and preventive care. It also reports a list of non-cancer conditions reported by the patient. Each recommendation includes a schedule and clear delineation of who is responsible. The plan of care also contains generic survivorship information, with a description of signs and symptoms to report to the oncology provider, contact information for the oncology provider, and recommendations to visit a primary care provider.

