**Figure 4 continued. Outcome collection**

Assessment	Source	Timing (including end of data collection window)
Survivor Post-Visit Survey	Patient	Following clinic visit, before leaving clinic
Primary Care Provider Survey	PCP	At least one week after being mailed Survivorship Care Plan, within a month of enrollment into study
Passively collected feasibility metrics	HN-STAR	Immediate concurrent data collection via Webcore
Nurse Practitioner Interview	NP	After 30 patients have completed Aim 1: Part 2 at MSK and 15 patients have completed Aim 1: Part 2 at HH, within 1 month of last patient completing Aim 1: Part 2 at the respective site
Survivor Follow-up Interview	Patient	Six months after the clinic visit
Preliminary metrics for future trial (Aim 2)		
Oncologic metrics: Late effects identified and addressed, receipt of head and neck surveillance and appropriate follow-up (e.g. dental exam for those who underwent radiation therapy)	Clinic notes, prescriptions or referrals	Abstracted from any time in the year before the visit (pretest) and in the note pertaining to the clinic visit (posttest)
Non-oncologic metrics: Receipt of routine preventive care (e.g., cancer screening, tobacco cessation)	Survivor Self-Assessment	After completion of the Survivor Self-Assessment

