**11.3.1 Oncologic outcomes.** We will only investigate late effects that we assess in HN-STAR. (If usability testing identifies additional late effects we did not target in our Survivor Self-Assessment, we will add them to the Survivor Self-Assessment for Aim 1: Part 2 and include them in Appendix H.) For each late effect, we will consider it identified if it was mentioned in a clinic note, and we will consider it addressed if there was a referral,

recommendation, education, or explicit acknowledgement of inaction. (Inaction may be appropriate, because in some cases, when symptoms are persistent and intractable, no intervention may be recommended.) For each patient, we will first count the number of late effects identified. We will then calculate the proportion of identified late effects that are addressed.

We will use descriptive statistics to report each element of oncologic care listed in Appendix H (i.e. smoking cessation, dental exam, blood work for thyroid studies, endoscopic exam, and head and neck physical exam). Each patient may not require every element of follow-up, depending on their primary tumor site or treatment received. We will use the number of recommended elements of care as the denominator, and we will calculate the proportion of these elements that are performed.

**11.3.2 Non-oncologic outcomes.** The non-oncologic outcomes in HN-STAR are collected only once. They include cancer screening, vaccination, and other preventive care elements that are explicitly collected in the Survivor Self-Assessment. Only some of these elements will be recommended for each patient, depending on their age, sex, and behaviors. We will calculate the proportion of recommended elements of non-oncologic care that are performed per patient. In addition, for each element of non-oncologic care, we will calculate the proportion of patients who receive it as recommended.

Findings from Aim 2 will inform whether these metrics can be collected from the EMR and HN-STAR. In addition, they will inform the statistical analysis for the future trial. For oncologic metrics only (Section 9.0, Figure 4), we will calculate the difference before HN-STAR use and after. Differences in oncologic metrics will be used in the power calculation for the proposed randomized trial. Non-oncologic metrics will be reported descriptively to inform the feasibility of collecting these data from self-report.

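### The surveillance score in 11.3.1 has no rule for whether an element is due, so with a one-year pretest and a one-visit posttest, on-schedule care biases the before-after difference downward

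*Combined protocol and SAP*

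**What the plan says.** Section 11.3.1 names the surveillance elements: "smoking cessation, dental exam, blood work for thyroid studies, endoscopic exam, and head and neck physical exam". It then says "Each patient may not require every element of follow-up, depending on their primary tumor site or treatment received", and defines the score: "We will use the number of recommended elements of care as the denominator", and "we will calculate the proportion of these elements that are performed". Neither recommended nor performed is defined further in the text.

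Figure 4 in Section 9.0 gives the two windows for oncologic metrics, which include surveillance: "Abstracted from any time in the year before the visit (pretest) and in the note pertaining to the clinic visit (posttest". Section 7.4.1 sets the same windows for surveillance specifically.

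At least one element is periodic. Section 4.2.3 gives as an example "annual thyroid studies for survivors who received radiation to neck". The tool also holds timing information. On the care plan, 4.2.4 says: "Each recommendation includes a schedule and clear delineation of who is responsible". Section 4.2.5 has the discussion guide present a surveillance schedule.

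The closing paragraph of 11.3.2 takes the before-after difference for oncologic metrics only and uses it in the power calculation for the randomized trial.

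**The concern.** The score asks whether a recommended element was performed in a window, but not whether it was due in that window. Over a full prior year, an annual test done on time will be found. In the note of a single visit it will be found only if it happened to fall due then. The same correct care therefore scores high before HN-STAR and lower after it.

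The plan recognises the parallel issue for late effects, where a documented decision to do nothing counts as addressing the problem. Surveillance has no corresponding provision.

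At stake is the surveillance difference among the 45 Aim 2 patients. If it partly reflects when tests fell due, it understates any gain from HN-STAR, and a planning effect for the future trial taken from it would be wrong.

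**Working it through.** The plan states no expected score, effect size or standard deviation for this metric, so there is no figure to reproduce. The check applies the written rule to a patient whose care is fully on schedule.

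**One patient, one element.** Thyroid studies are annual after neck radiation (4.2.3). Suppose they were done four months before the study visit. Pretest: 1/1. Posttest, read literally: 0/1. Nothing recommended was missed.

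**One patient, whole score.** With the five elements listed in 11.3.1 and one not due: 4/5 − 5/5 = −20 points. With four applicable elements and one not due: 3/4 − 4/4 = −25 points.

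**General form.** Let k be the number of recommended elements, all done on schedule in the prior year (pretest k/k = 100%). Let v of them be done at every visit. Let each of the remaining k − v be due at the study visit with probability q, and be done when due. Then

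posttest = (v + (k − v)q)/k, and difference = posttest − 1.

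The documents give none of k per patient, v or q, so these are assumptions shown over a range. Differences in percentage points:

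| k | v | q = 0 | q = 0.25 | q = 0.5 | q = 0.75 | q = 1 |
|---|---|---|---|---|---|---|
| 3 | 1 | −66.7 | −50.0 | −33.3 | −16.7 | 0 |
| 3 | 2 | −33.3 | −25.0 | −16.7 | −8.3 | 0 |
| 4 | 1 | −75.0 | −56.25 | −37.5 | −18.75 | 0 |
| 4 | 2 | −50.0 | −37.5 | −25.0 | −12.5 | 0 |
| 5 | 1 | −80.0 | −60.0 | −40.0 | −20.0 | 0 |
| 5 | 2 | −60.0 | −45.0 | −30.0 | −15.0 | 0 |

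For q from 0 to 0.75 the artefact runs from about −8 to −80 points. It vanishes only at q = 1.

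**Masking a real gain.** Take k = 4, v = 2, pretest 70%, and true performance of due elements under HN-STAR 80% (+10 points).
- q = 0.5: posttest = (2 × 0.8 + 2 × 0.5 × 0.8)/4 = 2.4/4 = 60%, a scored change of −10 points.
- q = 0.25: posttest = (2 × 0.8 + 2 × 0.25 × 0.8)/4 = 2.0/4 = 50%, a scored change of −20 points.

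The observed change need not be negative. With pretest 50%, true performance 70% and q = 0.5, posttest = (2 × 0.7 + 2 × 0.5 × 0.7)/4 = 2.1/4 = 52.5%, so a 20-point gain appears as +2.5.

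**With a due-only denominator.** The fully adherent patient scores 100% in both windows for every k, v and q in the table. In the masking example the score shows 80% − 70% = +10 points.

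**The case against.** The strongest reply is that 11.3.1 leaves its terms undefined. Tumor site and treatment are given as reasons why patients differ, not as an exhaustive list of filters, and recommended could mean recommended at that visit, since HN-STAR attaches a schedule to each recommendation. Appendix H, the abstraction form, may settle this, and its text is not available here. Figure 4 also names prescriptions and referrals as sources beside clinic notes, so a visit note that orders a test, or records a recent one, might count as performed. All of this stands as a limit on certainty. A reader might infer that the plan excludes due dates; it does not say so. It states one adjustment, no due rule, and windows that produce the artefact when the text is followed as written.

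A reader might also infer that the denominator is at fault independently of the windows. The documents do not support that. If one prior note were compared with the study note, an annual test could be missed on either side, and no systematic decline would follow. The downward direction needs the one-year pretest set against the one-visit posttest, and equal windows would largely remove it.

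Finally, the stakes are bounded. The study carries no formal test (11.1), this score is not among the feasibility criteria in 11.2, and Section 3.0 names late effects identified and late effects managed as the future trial's primary outcomes, with adherence to recommended care as a further question. That also stands. What remains is that 11.3.2 commits oncologic differences to the power calculation, and 11.4 says the trial will assess the Aim 2 outcomes.

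**Conclusion.** The point holds in this form: under the stated rule and the stated windows, the before-after difference in the surveillance score is biased downward by periodic care delivered on schedule before the visit. Only elements not done at every visit are affected. The loss is 20 points for a fully adherent patient with one of five elements not due, and zero if every periodic element falls due at the study visit.

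These figures illustrate the rule; they do not estimate the study's bias. It would be tempting to say that most annual tests will not be due at the visit, but that assumes random timing. The documents give no visit spacing, no adherence figures and no interval for the dental exam, and tests tied to routine visits could well fall due then. The conclusion also assumes that Appendix H contains no due rule. The matter should be corrected before the difference is used for planning; it does not affect the feasibility decisions.

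**What to change.** In 11.3.1, restrict the denominator in each window to elements that fell due in that window under the schedule HN-STAR already attaches to each recommendation:
- Pretest: elements that fell due in the prior year.
- Posttest: elements not already performed within their scheduled interval before the visit.

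Add the date last performed to the abstraction form. Apply one definition of performed to both windows, saying whether orders and referrals count. Use the resulting difference for the power calculation in 11.3.2. If Appendix H already contains such a rule, cite it in 11.3.1.

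Do not use as the effect measure an up-to-date score taken just before and just after the same visit: it can only stay level or rise, so any test done at the visit would register as gain. Nor is it the same quantity. With five elements, three current and two due, one of which is done, it gives 4/5 while the due-only score gives 1/2. It may be reported descriptively.

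The cost is slightly more abstraction from a prior-year record already being reviewed, and fewer elements per patient at posttest. Elements with an interval longer than the one-year look-back cannot always be classified and should be flagged as undetermined.

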## **12.1 RESEARCH PARTICIPANT REGISTRATION AND RANDOMIZATION PROCEDURES**

### **12.2 Research Participant Registration**

Confirm eligibility as defined in the section entitled Criteria for Patient/Subject Eligibility.

Obtain informed consent, by following procedures defined in section entitled Informed Consent Procedures.

During the registration process registering individuals will be required to complete a protocol specific Eligibility Checklist.

The individual signing the Eligibility Checklist is confirming whether or not the participant is eligible to enroll in the study. Study staff are responsible for ensuring that all institutional requirements necessary to enroll a participant to the study have been completed. See related Clinical Research Policy and Procedure #401 (Protocol Participant Registration).

### **12.3 Randomization**

Participants in this study will not be randomized.

## **13.1 DATA MANAGEMENT ISSUES**

### **13.1.1 Data and Source Documentation**

The participating site(s) will enter data remotely into an electronic database using the internet based systems, HN-STAR, which operates using Web Core. Data entry guidelines have been generated for this study and site staff will receive database training prior to enrolling its first participant. The participating site PI is responsible for ensuring these forms are completed accurately and in a timely manner. A schedule of required forms is shown in section 13.0.3. In addition, research staff at MSK will maintain a minimal CRDB dataset for both sites.

An RSA will be assigned to the study at each site. The responsibilities of the RSA include project compliance, data collection, abstraction and entry, data reporting, regulatory monitoring, problem resolution and prioritization, and coordinate the activities of the protocol study team.

Online data collected using the following study assessments at MSK and HH will be stored with Web Core as described in sections 7.1, and 7.2:

- Survivor Self-Assessment (Appendix A)
- Treatment Checklist (Appendix B)
- Survivor Post-Assessment Survey (Appendix D)
- Survivor Post-Visit Survey (Appendix E)
- Nurse Practitioner Post-Visit Survey (Appendix F)
- Primary Care Provider Survey (Appendix G)

Similarly, data collected during the NP Interview, the Survivor Post-Assessment Interview, and the Post-Visit Interview will be stored in a secure folder in the Department of Epidemiology & Biostatistics at MSK. Only study investigators and research staff at MSK will have access to the folder. All of the data will be identified by a unique participant identifier and the date of assessment.

Passively collected data described in section 7.3 will be recorded through the web interfaces of HN-STAR and in clinic notes. Some data from the following components will be collected passively:

- Treatment Checklist (Appendix B) (e.g., time required to complete or verify)
- Survivor Self- Assessment (Appendix A) (e.g., time required to complete, proportion completed)
- Clinic notes regarding late effects will be abstracted.

As described in section 7.4, the Medical Record Data Abstraction Form (Appendix H) will be completed by the RSAs at MSK and HH after each participant has completed participation. This Word document will be stored on secure folders at MSK and HH. Only investigators and research staff will have access to these folders. The completed Medical Record Data Abstraction Word document will be sent to MSK from HH using Sharebox.

### **13.1 Quality Assurance**

Registration reports will be generated to monitor patient accruals and completeness of registration data. The RSA will conduct monthly data quality scans to check the accuracy and completeness of data entry in HN-STAR and Medical Record Data Abstraction Forms. The principal investigator will regularly review registration report and data quality scans with the RSA.

In addition to registration reports and data quality scans, elements of the data process will be designed to minimize inaccuracies and inconsistencies and to maximize completeness. The databases created by HN-STAR will also be designed to automatically notify the person entering data when fields have been left blank or if the entry is out of a designated range.

Random-sample data quality and protocol compliance audits will be conducted by the study team on an annual basis.

### **13.2 Data and Safety Monitoring**

The Data Safety and Monitoring (DSM) Plans at Memorial Sloan Kettering Cancer Center were approved by the National Cancer Institute in September 2001. The plans address the new policies set forth by the NCI in a document entitled "Policy of the National Cancer Institute for Data and Safety Monitoring of Clinical Trials." The DSM Plans at MSK were established and are monitored by the Office of Clinical Research. The MSK Data and Safety Monitoring Plans can be found on the MSK Intranet at <https://one.mskcc.org/sites/pub/clinresearch/Documents/MSKCC%20Data%20and%20Safety%20Monitoring%20Plans.pdf>.

There are several different mechanisms by which clinical trials are monitored for data, safety and quality. There are institutional processes in place for quality assurance (e.g., protocol monitoring, compliance and data verification audits, therapeutic response, and staff education on clinical research quality assurance) and departmental procedures for quality controls, as well as two institutional committees that are responsible for monitoring the activities of our clinical trials programs. The committees – Data and Safety Monitoring Committee (DSMC) for Phase I and II clinical trials, and the Data and Safety Monitoring Board (DSMB) for Phase III clinical trials – report to the Center's Research Council and Institutional Review Board. During the protocol development review process, each protocol will be assessed for its level of risk and degree of monitoring required. Every type of protocol (e.g., NIH sponsored, in-house sponsored, industrial sponsored, NCI cooperative group, etc.) will be addressed and the monitoring procedures will be established at the time of protocol activation.

The Principal Investigator at MSK and site investigators will provide oversight and monitoring of all data collection. Forms will be kept in a secured location and will be available only to study members. The study team will have access to participants' PHI.

### **13.3 Regulatory Documentation**

Prior to implementing this protocol at MSK, the protocol, informed consent form, HIPAA authorization and any other information pertaining to participants must be approved by the MSK Institutional Review Board/Privacy Board (IRB/PB).

MSK Alliance sites will rely on the MSK IRB. Prior to implementing this protocol at a participating MSK Alliance site, all internal site approvals (e.g., HSP training and conflict of interest review) must be on file at MSK, and the MSK IRB must have granted approval for the site to open. Alliance site's compliance to Health Insurance Portability and Accountability Act (HIPAA) will be ensured by the Alliance site's privacy board.

Upon receipt of the required documents, MSK will formally contact the MSK Alliance site and grant permission to proceed with enrollment.

#### **Amendments**

Each change to the protocol document must be organized and approved by the MSK IRB/PB before changes can be implemented at the Alliance site.. Upon receipt of MSK IRB/PB approval, MSK will notify the MSK Alliance site.

#### **Continuing Review Approval**

The MSK IRB will review the study at least annually. The MSK primary site is responsible for submitting continuing review reports to the MSK IRB/PB.

#### **Deviations and Violations**

A protocol deviation on this study is defined as any incident involving noncompliance with an IRB approved protocol. Deviations typically do not have a significant effect on the rights, safety, or welfare of research participants or on the integrity of the resultant data. Deviations may be intentional or unintentional and they may be identified before or after they occur (prospective or retrospective).

A prospective deviation is any event that impacts eligibility, informed consent, or the intervention. For MSK sponsored multicenter studies, prospective deviations at the participating sites must be approved by the MSK IRB prior to implementation at the site; and reported to the site IRB according to site guidelines.

Retrospective deviations are all other deviations that do not adversely affect the rights, safety, or welfare of participants and do not result in a complete modification to the IRB approved protocol.

Retrospective deviations that represent non-compliance, unanticipated problems involving risks to participants or others, or serious adverse events will be reviewed in accordance with their respective policies and procedures. For MSK sponsored multicenter studies, retrospective deviations at the participating sites should be reported to the MSK IRB per the guidelines in this document and reported to the site IRB according to site guidelines.

